7.2.1.2 Special Guidelines Related to Oxaliplatin Toxicity

7.2.1.2.1 Dose Modifications for Neurological Toxicity Related to Oxaliplatin

Toxicity Grade	Duration of Toxicity		Persistent Between Cycles ^a
	1-7 Days	> 7 Days	
Grade 1 Paresthesias/dysesthesias ^b that do not interfere with function	Maintain dose	Maintain dose	Maintain dose
Grade 2 Tolerable Paresthesias/dysesthesias ^b interfering with function, but not activities of daily living (ADL)	Maintain dose	Maintain dose	Continue to dose but reduce to 80% of current dose ^c
Grade 2 Intolerable Paresthesias/dysesthesias ^b interfering with function, but not activities of daily living (ADL)	Hold until grade ≤1; then resume at 80% of current dose ^d	Hold until grade ≤1; then resume at 80% of current dose ^d	Hold until grade ≤1; then resume at 80% of current dose ^d
Grade 3 Paresthesias/dysesthesias ^b with pain or with functional impairment that also interfere with ADL	Hold until grade ≤1; then resume at 80% of current dose ^d	Hold until grade ≤1; then resume at 80% of current dose ^d	Hold until grade ≤1; then resume at 80% of current dose ^d
Grade 4 Persistent paresthesias/dysesthesias ^b that are disabling or life-threatening	Hold until grade ≤1; then resume at 60% of current dose ^d	Hold until grade ≤1; then resume at 60% of current dose ^d	Hold until grade ≤1; then resume at 60% of current dose ^d
ACUTE (during or after the 2 hour infusion) laryngopharyngeal dysesthesias ^b	1 st occurrence: Increase duration of next infusion to 4 hours ^d 2 nd and higher occurrence: Increase infusion to 6 hours	N/A	N/A

- Not resolved by the beginning of the next cycle.
- May be cold-induced.
- If grade 2 *tolerable* neurologic toxicity persists longer than 6 weeks, despite oxaliplatin dose adjustments, oxaliplatin should be held and therapy with capecitabine and pembrolizumab can be continued. If neurologic toxicity subsequently resolves to ≤ Grade 1, oxaliplatin therapy may resume at 80% of current dose.
- NOTE:** After Cycle 1, the treating physician may choose to hold oxaliplatin and continue capecitabine and pembrolizumab at current dose as clinically indicated. If toxicity resolves to grade 1 or less the treating physician may choose to restart oxaliplatin later in the patient's treatment course, the dose of oxaliplatin at which the patient restarts should be one dose level lower than last dose level on which patient was treated. The specific treatment approach used and dose modifications that occur are required to be reported in the Case Report Forms.

If grade 2 intolerable, grade 3 or grade 4 neurological toxicity (see Table 3E) is evident at the time of the next planned administration of oxaliplatin, then oxaliplatin administration will be held until the next treatment cycle. Capecitabine and pembrolizumab will be administered if otherwise appropriate.

Missed doses will not be made up. If toxicity resolves to grade 1 or less at next treatment cycle, resume oxaliplatin per instructions provided in Table 3E. If neurological toxicity is still present and has not resolved to grade 1 or less at the next treatment cycle, oxaliplatin will continue to be held. Patients may continue to receive capecitabine and pembrolizumab on study if otherwise appropriate.

Oxaliplatin may be repeatedly temporarily discontinued and then re-initiated in this fashion unless the patient has disease progression, whereby the patient will be removed from the study. However, if the patient is not receiving oxaliplatin at the time of progression, if it is appropriate and safe as determined by the treating physician that oxaliplatin can be restarted, oxaliplatin may be restarted and the patient may continue on treatment. If the patient has disease progression on oxaliplatin or it is not safe or appropriate to restart oxaliplatin, the patient will be removed from the study.

Dose escalations of oxaliplatin are not permitted at any time.

Laryngopharyngeal Dysesthesia

An unusual laryngopharyngeal dysesthesia (LPD), a loss of *sensation* of breathing without any *objective* evidence of respiratory distress (laryngospasm, bronchospasm or hypoxia) has also been observed. This neurotoxicity may be induced or exacerbated upon exposure to cold and should be distinguished from a hypersensitivity reaction. If a patient develops LPD, the patient's oxygen saturation should be evaluated via a pulse oximeter and, if normal, reassurance, a benzodiazepine or other anxiolytic agent should be considered and the patient should be observed in the clinic until the episode has resolved. The oxaliplatin infusion may then be continued at a reduced rate, 33% of the original rate. Because this syndrome may be associated with the rapidity of oxaliplatin infusion, subsequent doses of oxaliplatin should be administered as 4-6-hour infusions. To minimize the risk of LPD, patients will be instructed to avoid ice and cold drinks the day of treatment.

Hypersensitivity Reactions

Oxaliplatin, as is the case with all platinum-containing compounds, is associated with a measurable (approximately 11%) incidence of hypersensitivity reactions, usually after multiple doses of treatment. This may present as bronchospasm, hypotension, and even hemolytic anemia. Pre-treatment with glucocorticoids and anti-histamines may be useful for some patients, but may not always prevent the development of anaphylactoid reactions, especially in patients with a prior history of hypersensitivity to this agent. For patients who have experienced a Grade 1 or 2 acute hypersensitivity reaction that is assessed as related to oxaliplatin administration, the following premedication is recommended prior to each subsequent dose of oxaliplatin:

Dexamethasone 20 mg PO or IV, 12 and 6 hours prior to the oxaliplatin dose;
OR

Dexamethasone 20 mg PO or IV, as well as diphenhydramine 50 mg IV, and one of the following: cimetidine 300 mg IV, ranitidine 50 mg IV, or famotidine 20 mg IV 30-60 minutes prior to oxaliplatin administration.

If these prophylactic measures fail to prevent oxaliplatin-related hypersensitivity, therapy with oxaliplatin should be discontinued.

Patients who have grade 3 or 4 acute hypersensitivity reactions should discontinue oxaliplatin therapy.

Pulmonary Fibrosis

In the case of unexplained respiratory symptoms such as nonproductive cough, dyspnea or radiological pulmonary infiltrates, oxaliplatin should be discontinued until further investigation excludes

interstitial pulmonary fibrosis. If interstitial pulmonary fibrosis is confirmed, oxaliplatin therapy should be terminated.

7.2 Toxicity Management

Subjects should receive appropriate supportive care measures as deemed necessary by the Investigator. It may be necessary to perform conditional procedures such as bronchoscopy, endoscopy, or skin photography as part of evaluation of the event. Suggested supportive care measures for the management of adverse events with potential immunologic etiology are outlined below. Where appropriate, these guidelines include the use of oral or intravenous treatment with corticosteroids as well as additional anti-inflammatory agents if symptoms do not improve with administration of corticosteroids. Note that several courses of steroid tapering may be necessary as symptoms may worsen when the steroid dose is decreased. For each disorder, attempts should be made to rule out other causes such as metastatic disease or bacterial or viral infection, which might require additional supportive care. The treatment guidelines are intended to be applied when the Investigator determines the events to be related to pembrolizumab.

7.2.1 Pneumonitis

- For **Grade 2 events**, treat with systemic corticosteroids. When symptoms improve to Grade 1 or less, steroid taper should be started and continued over no less than 4 weeks.
- For recurrent **Grade 2 events**, discontinue treatment with pembrolizumab.
- For **Grade 3-4 events**, immediately treat with intravenous steroids. Administer additional anti-inflammatory measures, as needed.
- For first occurrence of **Grade 3-4 events**, discontinue treatment with pembrolizumab.

Add prophylactic antibiotics for opportunistic infections in the case of prolonged steroid administration.

7.2.2 Diarrhea/Colitis

Subjects should be carefully monitored for signs and symptoms of enterocolitis (such as diarrhea, abdominal pain, blood or mucus in stool, with or without fever) and of bowel perforation (such as peritoneal signs and ileus).

All subjects who experience diarrhea/colitis should be advised to drink liberal quantities of clear fluids. If sufficient oral fluid intake is not feasible, fluid and electrolytes should be substituted via IV infusion.

- For **Grade 2 or higher diarrhea**, consider GI consultation and endoscopy to confirm or rule out colitis.
- For **Grade 2** diarrhea/colitis that persists greater than 3 days, administer oral corticosteroids.
- For **Grade 3 or 4** diarrhea/colitis that persists > 1 week, treat with intravenous steroids followed by high dose oral steroids.
- When symptoms improve to Grade 1 or less, steroid taper should be started and continued over no less than 4 weeks.

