In addition, two important potential risks have been identified, although the data available thus far for these events does not provide sufficient evidence of a causal relationship to pembrolizumab. The two important potential risks are: a) myasthenic syndrome, and b) an increased risk of severe complications (such as early severe graft versus host disease and venoocclusive disease) of allogenic transplant in patients with hematologic malignancies who have previously been treated with PD-1 inhibitors. The Sponsor continues to monitor and collect data on these potential risks in order to further characterize their potential relationship to pembrolizumab.

Further details regarding reporting and management of immune-related AEs (irAEs) in general are described below.

In addition to the immune-related risks noted above, infusion-related reactions are also an important identified risk for pembrolizumab; however, they are not considered immune-mediated. Information regarding the nature and frequency of infusion-related reactions is included in the Reference Safety Information in Version 13 of the Investigator's Brochure (dated 17-Feb-2017).

Immune-Related Adverse Events

Based on the mechanism of action of pembrolizumab and similar immunomodulatory agents, the Sponsor is interested in all potential irAEs, and encourages appropriate investigation of signs and symptoms suggestive of these.

Consultation with the appropriate medical specialist should be considered when investigating a possible irAE. These events can occur after the first dose to several months after the last dose of treatment. Mild irAEs are usually treated symptomatically and infrequently require dosing delays or discontinuation. Higher grade and persistent lower grade irAEs typically necessitate withholding or discontinuing treatment and administration of systemic steroids or other immunosuppressive agents (such as tumor necrosis factor blockers), when systemic steroids are not effective. Early recognition of irAEs and initiation of treatment are critical to reduce the risk of complications, since the majority of irAEs are reversible with the use of steroids and other immune suppressants.

Table 1.2.1.3.1 All AEOSI Adverse Reactions Considered Expected for Pembrolizumab

Adverse Reaction	Frequencies	
	n	(%)
Rash pruritic	1	(0.0)
Rash pustular	1	(0.0)
Skin lesion	1	(0.0)
Stevens-Johnson Syndrome	1	(0.0)
Hepatitis	19	(0.7)
Autoimmune hepatitis	12	(0.4)
Hepatitis	6	(0.2)

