7.1.1 Pembrolizumab Dose Modifications

Adverse events (both non-serious and serious) associated with pembrolizumab exposure may represent an immunologic etiology. These adverse events may occur shortly after the first dose or several months after the last dose of treatment.

Pembrolizumab must be withheld for treatment-related toxicities as per Table 7.1.1. There are no dose reductions for pembrolizumab.

Note: Subject must be permanently discontinued for any severe or Grade 3 treatment-related toxicity that recurs or any life-threatening event unless otherwise specified in Table 7.1.1.

General Instructions:

1. Corticosteroid taper should be initiated upon AE improving to Grade 1 or less and continue to taper over at least 4 weeks.
2. For situations where pembrolizumab has been withheld, pembrolizumab can be resumed after AE has been reduced to Grade 1 or 0 and corticosteroid has been tapered. Pembrolizumab should be permanently discontinued if AE does not resolve within 12 weeks of last dose or corticosteroids cannot be reduced to ≤ 10 mg prednisone or equivalent per day within 12 weeks.
3. For severe and life-threatening irAEs, IV corticosteroid should be initiated first followed by oral steroid. Other immunosuppressive treatment should be initiated first followed by oral steroid. Other immunosuppressive treatment should be initiated if irAEs cannot be controlled by corticosteroids.

Table 7.1.1 Pembrolizumab Dose Modifications

Immune-related AEs	Toxicity grade or conditions (CTCAEv4.0)	Action taken to pembrolizumab	irAE management with corticosteroid and/or other therapies	Monitor and follow-up
Pneumonitis	Grade 2	Withhold	
 • Administer corticosteroids (initial dose of 1-2 mg/kg prednisone or equivalent) followed by taper 	
 • Monitor participants for signs and symptoms of pneumonitis • Evaluate participants with suspected pneumonitis with radiographic imaging and initiate corticosteroid treatment • Add prophylactic antibiotics for opportunistic infections
	Grade 3 or 4, or recurrent Grade 2	Permanently discontinue		

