Diarrhea / Colitis	Grade 2 or 3	Withhold	
 • Administer corticosteroids (initial dose of 1-2 mg/kg prednisone or equivalent) followed by taper 	
 • Monitor participants for signs and symptoms of enterocolitis (ie, diarrhea, abdominal pain, blood or mucus in stool with or without fever) and of bowel perforation
	Grade 4	Permanently discontinue		

Immune-related AEs	Toxicity grade or conditions (CTCAEv4.0)	Action taken to pembrolizumab	irAE management with corticosteroid and/or other therapies	Monitor and follow-up
				
(ie, peritoneal signs and ileus).
 
 Participants with \geq Grade 2 diarrhea suspecting colitis should consider GI consultation and performing endoscopy to rule out colitis. Participants with diarrhea/colitis should be advised to drink liberal quantities of clear fluids. If sufficient oral fluid intake is not feasible, fluid and electrolytes should be substituted via IV infusion.
AST / ALT elevation or Increased bilirubin	Grade 2	Withhold	Administer corticosteroids (initial dose of 0.5- 1 mg/kg prednisone or equivalent) followed by taper	Monitor with liver function tests (consider weekly or more frequently until liver enzyme value returned to baseline or is stable)
	Grade 3 or 4	Permanently discontinue	Administer corticosteroids (initial dose of 1-2 mg/kg prednisone or equivalent) followed by taper	
Type 1 diabetes mellitus (T1DM) or Hyperglycemia	Newly onset T1DM or Grade 3 or 4 hyperglycemia associated with evidence of β -cell failure	Withhold	
 Initiate insulin replacement therapy for participants with T1DM Administer anti-hyperglycemic in participants with hyperglycemia 	
 Monitor participants for hyperglycemia or other signs and symptoms of diabetes.
Hypophysitis	Grade 2	Withhold	
 Administer corticosteroids and initiate hormonal replacements as clinically indicated. 	
 Monitor for signs and symptoms of hypophysitis (including hypopituitarism and adrenal insufficiency)
	Grade 3 or 4	Withhold or permanently discontinue ¹		
Hyperthyroidism	Grade 2	Continue	Treat with non-selective beta-blockers (eg, propranolol) or thionamides as appropriate	
 Monitor for signs and symptoms of thyroid disorders.
	Grade 3 or 4	Withhold or permanently discontinue ¹		

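### Section 7.2.2 gives pembrolizumab-related Grade 3-4 diarrhea/colitis a longer wait for steroids than Grade 2, and its timing does not match Table 7.1.1

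*Combined protocol and SAP*

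**What the plan says.** Section 7.2.2 sets steroid timing by grade and duration. Its bullet on Grade 2 events has the wording "diarrhea/colitis that persists greater than 3 days, administer oral corticosteroids". The bullet on the two higher grades, 3 and 4, instead has "diarrhea/colitis that persists > 1 week, treat with intravenous steroids followed by high dose oral steroids". The GI consultation and endoscopy advice in the same section covers Grade 2 or higher and has no waiting period.

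The introduction to Section 7.2 fixes the status and scope of this advice. On status: "Suggested supportive care measures for the management of adverse events with potential immunologic etiology are outlined below". On scope: "The treatment guidelines are intended to be applied when the Investigator determines the events to be related to pembrolizumab". It also asks, for each disorder, that "attempts should be made to rule out other causes such as metastatic disease or bacterial or viral infection".

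Three other places bear on timing:

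- **Table 7.1.1, diarrhea/colitis row.** Pembrolizumab is withheld at Grade 2 or 3 and permanently discontinued at Grade 4. The steroid instruction is "Administer corticosteroids (initial dose of 1-2 mg/kg prednisone or equivalent) followed by taper". It gives neither a waiting period nor a route.
- **Section 7.1.1, general instruction 3.** "For severe and life-threatening irAEs, IV corticosteroid should be initiated first followed by oral steroid".
- **Section 1.2.1.3, on immune-related events in general.** "Early recognition of irAEs and initiation of treatment are critical to reduce the risk of complications".

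**The concern.** One would expect the threshold for starting steroids to fall, or at least not rise, as an immune-mediated event becomes more severe. Section 7.2.2 runs the other way. A site that takes its timing from that section alone could hold back steroids for over a week in a severe colitis already attributed to pembrolizumab, while treating a moderate one after three days.

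Section 1.2.1.3 lists colitis among the important identified risks of pembrolizumab, and Section 7.2.2 itself tells sites to watch for bowel perforation. What is at stake is the timing of one treatment for one toxicity. The efficacy analysis is not involved.

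**Working it through.** The plan gives no statistical figure to reproduce here. The check compares the texts.

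**Step 1. Set the timings side by side.**

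| Place | Grade 2 | Grade 3 | Grade 4 |
|---|---|---|---|
| Section 7.2.2 | oral, after more than 3 days | IV then high-dose oral, after more than 7 days | as Grade 3 |
| Table 7.1.1 | 1-2 mg/kg, no wait stated | 1-2 mg/kg, no wait stated | probably the same (step 3) |
| General instruction 3 | not addressed | IV before oral, no timing stated | IV before oral, no timing stated |

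Within Section 7.2.2 the two waits differ by 7 − 3 = 4 days, with the longer one at the higher grades. This compares start times only, because the two regimens differ (oral against IV followed by high-dose oral).

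**Step 2. Could the 3-day bullet also cover Grade 3-4, with IV steroids as a later escalation?** The bullet names Grade 2. The bullet directly above it is written for Grade 2 or higher, so the section separates the two ranges. On its wording, Section 7.2.2 has no steroid instruction for a Grade 3 or 4 event lasting one week or less.

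**Step 3. Compare with Table 7.1.1.** The row gives a starting dose and a taper with no persistence condition. This is explicit for Grade 2 or 3. In the text available, the Grade 4 steroid cell is empty, probably because one cell spans both lines. Where the table intends different steroid doses by grade, as in the AST/ALT row, it prints them separately. Grade 4 coverage is therefore a reasonable inference from layout. The timing mismatch also reaches Grade 2, where Section 7.2.2 has a 3-day wait and the table has none.

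**Step 4. Look for a reason for the wait.** Capecitabine also causes diarrhea (Section 1.2.3), so time to establish the cause is a natural candidate. Two things count against it. Section 7.2 applies once the investigator has already judged the event related to pembrolizumab. And uncertainty about cause would not explain a shorter wait at Grade 2. Section 7.1.2.1.1 also works on a faster clock: it advises considering a diagnostic evaluation if control takes longer than 2 days, and *C. difficile* evaluation at Grade 3 or above.

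**Step 5. Gauge how many patients this could touch.** The documents give no Grade 3-4 rate of pembrolizumab-related diarrhea/colitis for this combination. Section 1.2.1.3 gives 48 colitis cases of any grade in a pembrolizumab reference dataset of 2,799 subjects:

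- 48 / 2,799 = 1.7%
- 35 × 0.017 ≈ 0.6 expected cases of any grade

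Grade 3-4 would be a subset of these. Against that, the rate with chemotherapy could be higher, and diarrhea not coded as colitis is left out.

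**The case against.** The best case for the plan is that much is left to clinical judgment. The Section 7.2 measures are suggestions, nothing in Section 7.2.2 bars earlier steroids, and Section 7.0 asks for supportive care at the first signs of related toxicity. Drug holds, hydration and GI work-up do not wait for the steroid trigger, and Section 5.7 calls for stopping pembrolizumab for attributed Grade 3 diarrhea or colitis whatever its duration. Table 7.1.1 could be read as supplying the dose and Section 7.2.2 the timing. With capecitabine in the regimen, some persistence condition for diarrhea is not odd in itself.

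Most of this stands, and it limits the consequence. It does not explain why the wait is longer at the higher grade. Reading the table for dose and Section 7.2.2 for timing would settle the mismatch in favor of the inverted waits.

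A reader might also infer that Section 7.2.2 contradicts general instruction 3. The documents do not support that: the instruction sets the order of routes, IV before oral, which Section 7.2.2 follows, and it is silent on when to start. The Section 1.2.1.3 statement is general background on immune-related events. The inverted wait sits badly with it but breaks no management rule there. Nor does it add much that other organ toxicities in Section 7.2 carry no such wait, since they lack diarrhea's obvious chemotherapy alternative.

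**Conclusion.** The point holds as an inconsistency in safety guidance. Section 7.2.2 attaches the longer steroid wait to the more severe event, leaves Grade 3-4 events of one week or less without a steroid instruction in that section, and does not match the timing in Table 7.1.1. The table mismatch is firm for Grade 2 and 3 and rests on inferred layout for Grade 4.

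The likely scale is small: about 0.6 any-grade colitis cases among 35 patients, if the reference-dataset frequency carries over to this combination. That is an assumption, and the true number could be higher.

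Two stronger readings are tempting and should be resisted. One is that the protocol forbids steroids, or leaves severe colitis unmanaged, for a week. It does neither. The other is that the trial's results are compromised. The PFS endpoint, the sample size and every planned analysis are untouched. The case for correction is patient safety, and the correction is cheap.

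**What to change.** In the Grade 3 or 4 bullet of Section 7.2.2, replace the one-week persistence condition with *judged related to pembrolizumab*. IV steroids followed by high-dose oral steroids would then start without a waiting period. Infectious causes, including *C. difficile*, should be evaluated alongside, as Sections 7.1.2.1.1 and 7.2 already recommend.

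State the same timing in the diarrhea/colitis row of Table 7.1.1, and make its Grade 4 coverage explicit. If the sponsor keeps the Grade 2 wait of more than 3 days, add it to that row so that the two places agree. Pointing to general instruction 3 would not settle the timing, because it states none. Leave the Section 5.7 discontinuation rules unchanged.

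The cost is protocol wording and a clarification letter to sites, with no new visits, tests or analyses. The clinical downside is that a few patients whose severe diarrhea is in fact due to chemotherapy may receive steroids earlier than they would now.
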